## 7.2 Drug studies:

AGENT	DOSE	ROUTE	DAYS	NOTES
Prunes	4 oz/day	PO	3	Participant to eat any time during the day

## 7.3 Criteria for removal from treatment:

7.31 Unable to tolerate eating prunes.

7.32 A participant may always be removed from treatment whenever she wishes.

7.33 Bowel complications including ileus, obstruction, delayed recognition of bowel injury.

7.34 NPO status recommended by supervising physician.

## 8.0 ASSESSMENT OF EFFICACY AND SAFETY

### 8.1 Side effects/Toxicities to be monitored.

8.11 Prunes have a favorable safety profile, but mild, transitory gastrointestinal cramping, flatulence, pains, or diarrhea may occur.

8.12 No long-term toxicities to monitor after completion of therapy.

8.2 No formal dosage change will take place based on toxicity as associated with prunes. However, participants will be instructed that they may reduce their prune consumption or discontinue prune consumption if they experience side effects.

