### 8.3 Adverse Event Reporting:

8.31 Patient will be advised to tell study physician if she feels that she has been injured because of taking part in this study.

8.32 The PI will appropriately report all adverse events to the IRB.

8.4 Data Monitoring Committee: All injuries believed by the treating medical doctor to be due to participation in this study will be reviewed by the Data Monitoring Committee of USC.

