#### 10.0 CRITERIA FOR EVALUATION AND ENDPOINT DEFINITIONS

The outcome status of all eligible patients will be reported. All eligible patients who begin treatment will be included in the analysis.

Primary endpoints: Time to first bowel movement (in hours)

Secondary endpoints:

1. Stool consistency of the first bowel movement as classified by the Bristol Stool Scale (The stool types are categorical variables, and we will evaluate the differences in the frequencies of the responses by treatment status with a chi-square test)
2. Pain with bowel movement measured (Likert scale, and assessed using t-test or non-parametric methods as appropriate)
3. Satisfaction with bowel regimen (Likert scale, and assessed using t-test or non-parametric methods as appropriate)
4. Satisfaction with surgery overall (Likert scale, and assessed using t-test or non-parametric methods as appropriate)
5. Requirements for laxative (yes or no, assessed as categorical variables and evaluated by chi-square test)
6. Compliance with docusate (percentage of medications consumed, and assessed using t-test or non-parametric methods as appropriate)
7. Compliance with prunes (percentage of prunes consumed, and assessed using t-test or non-parametric methods as appropriate)

8. Adverse events of extreme bloating or flatulence (yes or no, assessed as categorical variables and evaluated by chi-square test)

Compliance with prune consumption will be defined as reported successful consumption of 2/3 of the assigned prunes.

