# Prunes Data Collection Sheet

## Self administered survey

Have you had a bowel movement since surgery? Yes No

If Yes, When did you have your first bowel movement?

Date \_\_\_\_\_ Time \_\_\_\_\_

How *painful* was your first bowel movement?

Not at all painful 0    1    2    3    4    5    6    7    8    9    10 Very painful

Which picture best describes your bowel movement (Circle one number)?

1    2    3    4    5    6    7

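### The mild side effects that section 8.1 says will be monitored are not systematically collected: the one harm endpoint names other or more severe effects, and no participant form has an item for any of them.

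*Combined protocol and SAP*

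**What the plan says.** Section 8.1 is headed "Side effects/Toxicities to be monitored". Item 8.11 calls the safety profile of prunes favorable but says that "mild, transitory gastrointestinal cramping, flatulence, pains, or diarrhea may occur".

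Section 8.2 makes no formal dosage change for toxicity, but "participants will be instructed that they may reduce their prune consumption or discontinue prune consumption if they experience side effects". Section 7.3 (item 7.31) lists inability to tolerate prunes as a criterion for removal, separate from the participant's own wish (7.32).

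Among the secondary endpoints in section 10.0, the only one that concerns harm is number 8: "Adverse events of extreme bloating or flatulence (yes or no, assessed as categorical variables and evaluated by chi-square test"). Section 3.6 says that participants will answer whether they experienced the secondary outcomes.

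Adverse event reporting in section 8.3 has two parts: "Patient will be advised to tell study physician if she feels that she has been injured because of taking part in this study" (8.31), and "The PI will appropriately report all adverse events to the IRB" (8.32).

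**The concern.** A plan that names the effects it expects should have somewhere to write them down. Here the expected effects (four gastrointestinal symptoms, mild and short-lived) and the harm endpoint (bloating or flatulence, at least partly restricted to an extreme degree) barely overlap, and the forms do not appear to record either.

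The trial asks whether prunes should be added to docusate. A shorter time to first bowel movement has to be weighed against how well women tolerate the addition. If symptoms are not asked about in the same way in both arms, a statement that harms did not differ may reflect what was asked rather than what happened. A woman who cut back because of cramps would also look the same on the prune count as one who did not care for prunes.

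**Working it through.** **Step 1. The effects in 8.1 set against the endpoint and the forms.** The forms checked are the data collection sheets and self-administered survey (Appendix III, English and Spanish), the prune diary (Appendix IV) and the stool softener diary (Appendix V).

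| Effect | In 8.1 | In endpoint 8 | Own item on survey or diary | Nearest measure compared by arm |
|---|---|---|---|---|
| Cramping | yes | no | no | none specific |
| Pains | yes | no | no | 0-10 pain, first bowel movement only |
| Diarrhea | yes | no | no | Bristol type, first bowel movement only |
| Flatulence | yes (mild) | yes (degree depends on reading) | no | none specific |
| Bloating | no | yes (extreme) | no | none specific |

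Of the four effects in 8.1, one is in endpoint 8 and none has its own item. Of the two components of endpoint 8, neither has an item.

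**Step 2. What the forms do ask.** The survey covers the time of the first bowel movement, its pain ("How *painful* was your first bowel movement") and Bristol type, two satisfaction scores, docusate and prune counts for days 1 to 3, and laxative use. The diaries record times of intake only. No item asks why fewer prunes were eaten.

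**Step 3. How far the proxies reach.** Prunes are given for three days (section 7.2), but stool form and pain are recorded for a single bowel movement, so loose stools after the first are not seen. Pain on passing stool is not abdominal cramping. Both items are also outcomes of the regimen, so a looser first stool may be read as benefit. Satisfaction with the regimen may fall when tolerability is poor, but it does not say why.

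**Step 4. The unsolicited routes.** Item 8.31 depends on a woman feeling that she was injured, which mild cramping is unlikely to prompt. Item 8.32 sends adverse events to the IRB. The telephone call in section 3.6 asks whether the sheets were mailed and refers any concerns to triage. None of these has a stated summary by arm, and no placebo is described.

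**Step 5. What collection would yield.** Section 13.0 gives 63 per group for a 12-hour difference, SD 23.7, 80% power and two-sided 0.05. Reproduced: 2 × (1.960 + 0.842)² × (23.7/12)² = 2 × 7.85 × 3.90 = 61.2, so 62 by the normal approximation. The t-based solution is 62.2, so 63. Allowing for 10% attrition, 63/0.9 = 70. I take 63 per arm as the number evaluable.

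The documents give no symptom rates, so the rates below are assumptions. The 95% CI is d ± 1.96 × √{[p₁(1−p₁) + p₂(1−p₂)]/63}.

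- 10% versus 20%: √(0.25/63) = 0.063; 0.10 ± 0.123; about -2 to 22 points.
- 15% versus 30%: √(0.3375/63) = 0.073; 0.15 ± 0.143; about 1 to 29 points.
- 10% versus 30%: √(0.30/63) = 0.069; 0.20 ± 0.135; about 6 to 34 points.

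In terms of power, 63 per arm gives about 80% (two-sided 0.05) for 5% versus 22%, 10% versus 30%, 20% versus 43%, or 30% versus 55%.

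**The case against.** The best defence is that this is a three-day food intervention with a favorable safety profile. Saying that effects will be monitored does not promise a test between arms, and limiting a formal comparison to marked symptoms is a reasonable choice. That stands, and it is why the fix asks for description rather than more tests. It does not explain why no form collects the symptoms, including those in endpoint 8.

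Four stronger readings are tempting, and the documents do not support them:

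- *The expected harms cannot be compared at all.* Bristol type (types 6 and 7 are mushy or liquid) and pain at the first bowel movement are compared by arm and touch on diarrhea and pains.
- *Poor tolerability could show only as low compliance.* Satisfaction with the regimen is scored 0-10 in both arms and compared, and 7.31 treats intolerance as its own reason for removal. Neither isolates the symptom, and no form item records the 7.31 reason, but both exist.
- *Flatulence counts only when extreme.* In the wording of endpoint 8, the adjective may apply to bloating alone. Cramping, pains and diarrhea are absent on either reading.
- *The trial would clearly detect a doubling of symptoms if it asked about them.* From an assumed 10%, doubling gives an interval that includes zero. Only from a higher base rate, such as 15%, does it just exclude zero.

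It is also fair to object that women who know their arm may report mild symptoms differently, and that a composite of any symptom could be swamped by ordinary postoperative complaints in both arms. The first remains a limitation of any fix. The second is met by reporting each symptom separately.

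**Conclusion.** The point holds as a gap in collection as much as in definition. None of the four effects in 8.1 has a dedicated item, only one of them is named in endpoint 8, and endpoint 8 itself has no field on the forms, although section 3.6 says that participants will answer on the secondary outcomes. Followed as written, the plan gives partial proxies tied to one bowel movement, a general satisfaction score, and unsolicited reports with no planned summary by arm. That is not a fair comparison of the harms it says it will monitor.

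The change should be made, but it does not touch the primary endpoint or the sample size. The conclusion assumes that Appendices III to V are the complete participant-facing data forms. The precision figures assume 63 evaluable women per arm and symptom rates that the documents do not supply.

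**What to change.** **Survey.** On the existing English and Spanish surveys, in identical words for both arms, add four items covering days 1-3: cramping or abdominal pain; diarrhea; bloating; flatulence. Each is rated none, mild, moderate or severe. For the prune arm only, add one item: if you ate fewer than the assigned prunes, why (side effect, did not want them, other)?

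**Endpoint 8.** Align it with section 8.1 by defining it as these symptoms over days 1-3. Report each separately by arm and severity, with the difference in proportions and its 95% CI, and not only as a composite of any symptom. Keep severe bloating or flatulence as the component that carries over from the present definition.

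**Adverse events.** Summarize unsolicited reports by arm as well, stating that they were unsolicited.

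**Cost.** Four short items, one reason item and their Spanish versions, and a revised endpoint definition. The downsides are a slightly longer survey, more descriptive secondary comparisons, open-label reporting bias that the items cannot remove, and wide intervals, so moderate differences will have to be described rather than tested. Rewording endpoint 8 without adding the items would achieve nothing.

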### 8.3 Adverse Event Reporting:

8.31 Patient will be advised to tell study physician if she feels that she has been injured because of taking part in this study.

8.32 The PI will appropriately report all adverse events to the IRB.

8.4 Data Monitoring Committee: All injuries believed by the treating medical doctor to be due to participation in this study will be reviewed by the Data Monitoring Committee of USC.

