### 3.6 Evaluation Post-Intervention:

1. All participants will record the date and time of, consistency of and pain associated with their first bowel movement, and answer whether they experienced secondary outcomes as described later.

2. Participants in the treatment arm will also log the number of prunes consumed each day.

2. Participants will be given a stamped and addressed envelope to return the data collection sheets in. Participants will receive a call from an investigator masked to the treatment allocation on postoperative day 3 inquiring about whether the participant has mailed the data collection sheets back. Those who do not answer will be called again the next day.

3. During the phone call, if the participant indicates any postoperative concerns, she will be instructed to contact the on call physician at the LAC+USC Ob/Gyn Triage.

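### Patient reports and committee review are limited to harms blamed on participation, and no visible form collects the plan's own adverse-event endpoint or the bowel complications it names

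*Combined protocol and SAP*

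**What the plan says.** The protocol deals with harms in five places.

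- Section 8.31, on what the participant is told: "Patient will be advised to tell study physician if she feels that she has been injured because of taking part" in the study.
- Section 8.32, on reporting: "The PI will appropriately report all adverse events to the IRB".
- Section 8.4, on the Data Monitoring Committee: "All injuries believed by the treating medical doctor to be due to participation in this study will be reviewed" by it.
- Section 10.0, secondary endpoint 8: "Adverse events of extreme bloating or flatulence (yes or no, assessed as categorical variables and evaluated by chi-square test".
- Section 7.33, a criterion for removal from treatment: "Bowel complications including ileus, obstruction, delayed recognition of bowel injury".

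The scheduled telephone call (section 3.6) is made by an investigator masked to allocation. Its stated purpose is to ask whether the sheets have been mailed. On concerns it says only this: "if the participant indicates any postoperative concerns, she will be instructed to contact the on call physician".

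Section 3.6 also says that all participants will answer whether they had the secondary outcomes.

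**The concern.** Participants know their allocation. Section 3.5 gives one arm a package of prunes, section 6.3 tells the other to avoid prune products, and no placebo is described. Section 8.2 ties the advice about side effects to cutting down or stopping prunes. Controls receive docusate as existing routine care, so a control participant has little study-specific treatment to blame for a bowel problem. A reporting rule that depends on perceived cause can therefore work differently in the two arms.

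Two things are at stake. Endpoint 8 is a prespecified comparison by arm and needs a data item. The complications in section 7.33 are the serious bowel events that the protocol itself names, and an arm-comparable count of them would be expected at the end of a trial whose background (section 1.2) suggests that prunes can be a safe addition.

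**Working it through.** **Step 1. Set each provision beside its means of collection.**

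| Provision | Conditional on believed cause? | What it governs | Visible collection item |
|---|---|---|---|
| 8.31 | Yes, the participant's belief | What she is advised to report | None; she must volunteer it |
| 8.32 | No | What the PI sends to the IRB | None |
| 8.4 | Yes, the treating doctor's belief | What the committee reviews | None |
| 10.0, endpoint 8 | No | Chi-square comparison by arm | None |
| 7.33 | No | Removal from treatment | None |
| 3.6, call | No | Referral of concerns to triage | No recording step stated |

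**Step 2. Go through the forms in Appendices III to V and the calendar in section 9.0.**

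- The randomization sheet records enterotomy or bowel surgery at operation, and inability to start oral intake. Both precede study treatment.
- The postoperative day 3 sheet shows day and time of discharge.
- The self-administered survey, in English and Spanish, covers the first bowel movement, its pain and stool type, two satisfaction scales, docusate, laxatives and prunes. The Bristol item can show a liquid first stool, but it does not ask about diarrhea. There is no item on bloating, flatulence or cramping.
- The two diaries log intake.
- The calendar has no adverse-event row.

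So section 3.6 promises answers on the secondary outcomes, but the survey lacks the question for endpoint 8. Section 8.32 states a duty to report onward and does not say how the PI learns of an event that nobody attributed to the study.

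**Step 3. What can be computed.** The plan states no adverse-event rate and no safety power. Its only sample size is for time to first bowel movement (difference 12 hours, SD 23.7, 80% power, two-sided 0.05). A t-test calculation gives 62.2, rounded up to 63 per group, and 63 / 0.90 = 70. The stated figures reproduce and do not depend on this point.

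**Step 4. Illustration with assumed figures.** Let the true event rate p be the same in both arms, with a fraction c1 captured under prunes and c0 under control. The observed risk ratio is (p × c1) / (p × c0) = c1 / c0. The event rate cancels, so the ratio is whatever one assumes about capture:

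- 80% against 60%: 0.80 / 0.60 = 1.33
- 80% against 40%: 0.80 / 0.40 = 2.0
- 40% against 80%: 0.40 / 0.80 = 0.5

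Suppose an outcome compared by arm had to be filled from volunteered reports, with 63 per arm. Put a = p × c1, b = p × c0 and m = (a + b) / 2. The chance of a significant difference when none exists is about Φ{[|a − b|√63 − 1.96√(2m(1 − m))] / √[a(1 − a) + b(1 − b)]}.

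| Assumed true rate | Capture 80% vs 60% | Capture 80% vs 40% |
|---|---|---|
| 10% | 6% | 15% |
| 20% | 9% | 28% |
| 30% | 13% | 42% |

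The nominal level is 5%.

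**Step 5. Rare events, again with assumed rates.** The chance of recording at least one case in an arm of 63 is 1 − (1 − p)^63. At 1%, 2% and 5% this is 47%, 72% and 96%. If only half the cases are captured, p is replaced by p/2 and the chances fall to 27%, 47% and 80%.

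**The case against.** The strongest reply is that the plan does not filter everything by attribution. Section 8.32 covers all adverse events, endpoint 8 has no causal condition, section 3.6 says participants will answer on secondary outcomes, and section 8.4 defines what the committee reviews, not what is collected. All of this stands. A reader might infer that events reach the study only if someone blames participation; the text does not support that. What remains is that these unconditional provisions have no visible item behind them.

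A reader might also infer that both the participant and her treating doctor know the arm. The documents establish this for the participant. They do not say whether the treating or on-call physician knows it.

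Safety is not among the objectives in section 2.0, and the numbers are small. Even with perfect capture and no cases in 63 women, the one-sided 95% upper limit is 1 − 0.05^(1/63) = 4.6%. Incomplete recording is thus not the main reason why the trial could say little about rare complications. That is fair, but it does not excuse a prespecified endpoint without a data item.

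The consent form is not among the pages available, and it may contain instructions on reporting harms. Such instructions would not supply a data field. The PI may also hear of events through the hospital, but no section provides for it.

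**Conclusion.** The point holds in this form. Two routes (8.31 and 8.4) depend on believed cause in a trial where participants know their arm. The two provisions without that condition (8.32 and endpoint 8) have no visible means of collection in either arm, and neither do the complications in 7.33. As written, endpoint 8 cannot be analysed from the forms shown, and bowel complications may go unrecorded or be reported differently by arm.

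It would go too far to say that harms are counted unequally. That is a risk, not a fact in the documents. Reporting could favour either arm, or nothing might be reported at all. Any single figure for the distortion, such as a tenfold excess from assuming 50% attribution in one arm and 5% in the other, only restates the assumption (0.50 / 0.05 = 10).

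The conclusion rests on the forms and sections available. It does not touch the stated sample size. It is a gap worth closing because the remedy is cheap.

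**What to change.** 1. Remove the attribution condition from 8.31 and 8.4, so that events are recorded in both arms whatever the believed cause and the committee reviews them by arm.
2. Add identical yes/no items for both arms to the existing self-administered survey, in English and Spanish: extreme bloating, flatulence, cramping, diarrhea, and unplanned triage visit or readmission. This gives endpoint 8 its data source and covers side effects that section 8.11 lists.
3. Add to the existing postoperative day 3 sheet: ileus, obstruction, recognised bowel injury, NPO status, and removal from treatment with date and reason. Study staff other than the masked caller should complete it, because a reason such as inability to tolerate prunes (7.31) would reveal the arm.
4. Have the caller log any concern referred to triage and pass it to the PI.

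The cost is a wording amendment, a slightly longer survey and day 3 sheet, some staff time, and more unrelated events to log. No visit, procedure or treatment rule changes.

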#### 9.0 CLINICAL AND LABORATORY EVALUATIONS AND STUDY CALENDAR

Parameter	Pre-Treatment	Postoperative day 1	Postoperative day 3*	Postoperative day 5*
Targeted history	X			
Operative history		X		
Postoperative Data Collection Sheet to be Mailed-In			X	X

\* If unable to reach patient by the telephone on postoperative day 3, another attempt will be made on postoperative day 5.

#### 10.0 CRITERIA FOR EVALUATION AND ENDPOINT DEFINITIONS

The outcome status of all eligible patients will be reported. All eligible patients who begin treatment will be included in the analysis.

Primary endpoints: Time to first bowel movement (in hours)

Secondary endpoints:

1. Stool consistency of the first bowel movement as classified by the Bristol Stool Scale (The stool types are categorical variables, and we will evaluate the differences in the frequencies of the responses by treatment status with a chi-square test)
2. Pain with bowel movement measured (Likert scale, and assessed using t-test or non-parametric methods as appropriate)
3. Satisfaction with bowel regimen (Likert scale, and assessed using t-test or non-parametric methods as appropriate)
4. Satisfaction with surgery overall (Likert scale, and assessed using t-test or non-parametric methods as appropriate)
5. Requirements for laxative (yes or no, assessed as categorical variables and evaluated by chi-square test)
6. Compliance with docusate (percentage of medications consumed, and assessed using t-test or non-parametric methods as appropriate)
7. Compliance with prunes (percentage of prunes consumed, and assessed using t-test or non-parametric methods as appropriate)

8. Adverse events of extreme bloating or flatulence (yes or no, assessed as categorical variables and evaluated by chi-square test)

Compliance with prune consumption will be defined as reported successful consumption of 2/3 of the assigned prunes.

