## 2.0 OBJECTIVES AND PURPOSE

2.1 To determine the time to first bowel movement after benign gynecological surgery in women treated with prunes and docusate compared to those treated with docusate alone.

2.2 To determine pain associated with first bowel movement (scale 1-10), stool consistency using Bristol stool form scale, the need for additional laxatives, compliance and patient satisfaction.

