## 3.0 STUDY DESIGN

3.1 This is a prospective, randomized control trial.

3.2 Identification of Subjects:

All potential participants will be identified in the Gynecology or UroGynecology clinic at Los Angeles County-University of Southern California (LAC+USC) Medical Center. On average, between 8-10 patients undergo benign gynecologic surgery with overnight stay per week.

3.3 Recruitment of Participants:

Each eligible participant will be approached in person by one of the study investigators and invited to participate in the study. The informed consent will be reviewed in detail with a physician and the potential participant will be given time to ask questions. The potential participant will be allowed to take a copy of the consent home to review and discuss with family or friends.

3.4 Evaluation Pre-Intervention:

Clinical information will be collected.

3.5 Intervention:

1. Participants that undergo benign gynecologic surgery without intraoperative complications that are admitted overnight will be randomized to one of two groups.

2. Participants in the treatment arm will receive a 12 oz package of prunes on the morning of postoperative day 1.

3. All participants will receive the standard 100 g docusate sodium twice daily. Participants in the treatment arm will be instructed to consume 4 oz prunes (12 prunes) daily.

4. Additional laxatives will not be routinely given. There will be additional laxative medications (Milk of Magnesia) available for participants as needed, and it will be recorded that additional laxatives were needed.

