## 6.0 STRATIFICATION/DESCRIPTIVE FACTORS/RANDOMIZATION SCHEME

6.1 Stratification factors. N/A

6.2 Descriptive factors. Age, height, weight, self-described race and ethnicity, menopausal status, baseline frequency of bowel movements, laxative use, fiber use, medications used, and baseline stool consistency.

6.3 Randomization plan:

On morning of post-operative day 1, participants who do not meet exclusion criteria will be randomized to the treatment or control group at a 1:1 ratio. Randomization blocks of 6 will be applied in this study to ensure balanced treatment assignments throughout the recruitment period. The randomization assignment list will be generated by the study statisticians. [name]. Ph.D

Participants will be standardly administered 100 g of docusate twice daily for three days per existing routine post-operative care. In addition, we will administer a total of 12 oz of prunes to the study group which are pitted and preservative free. The prunes will be provided to the participant in a sealed package. The study group be instructed to eat 4 oz of prunes daily. The control group will be advised to avoid prune products for 3 days. Each group will be given a diary to note their prune and/or docusate consumption and details of their first bowel movement.

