#### 13.0 STATISTICAL CONSIDERATIONS

The sample size of 63 participants per treatment group was calculated to detect a clinically significant mean difference in time to first bowel movement of 12 hours using a two-sample t-test with a standard deviation of 23.7 at 80% power and two-sided significance level of  $p=0.05$ . The sample size was inflated to 70 participants per group to account for an estimated 10% attrition rate.

Summaries of participant characteristics will be described by treatment arm. Participant characteristics will be presented as means and standard deviations for continuous variables and counts and percentages for categorical variables. Comparisons of baseline characteristics will be assessed using two-sample t-tests or the non-parametric corollary for continuous variables and chi-square test for categorical variables. The primary outcome, a comparison of the time to first bowel movement between the treatment and control groups, will be assessed using two-sample t-tests. The secondary outcome, pain at first BM, will also be evaluated using two sample t-tests.

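### The only analysis-set rule depends on an undefined post-randomisation event, beginning treatment, and can be read as dropping women who ate no prunes from the prune arm alone; the likely bias is small, and one sentence fixes it

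*Combined protocol and SAP*

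**What the plan says.** Section 10.0 states: "All eligible patients who begin treatment will be included in the analysis". The sentence before it promises that outcome status will be reported for all eligible patients, but that is a promise to report and does not define who enters the primary comparison. Section 13.0 describes the primary analysis as a "comparison of the time to first bowel movement between the treatment and control groups" by t-test and names no population. Neither section says that all randomised women are analysed as assigned.

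Under section 6.3, on the morning of postoperative day 1, "participants who do not meet exclusion criteria will be randomized to the treatment or control group at a 1:1 ratio". Allocation is then evident to the woman. Section 3.5 says "Participants in the treatment arm will receive a 12 oz package of prunes on the morning of postoperative day 1", and the text after 6.3 says "The control group will be advised to avoid prune products for 3 days". No placebo is described, and the only masking mentioned is of the telephone caller in section 3.6. The documents do not use the word open-label; it is inferred from this design.

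**The concern.** A woman either begins treatment or does not after she has been randomised and knows her arm. If beginning means eating at least one prune in the prune arm, the condition can remove women from that arm and has no counterpart among controls. The primary comparison would then no longer be between the groups as randomised.

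The bias could go either way. It would favour prunes if women who never start, for example because of nausea, also recover bowel function more slowly. It would count against prunes if they skip them because their bowels have already moved. An analyst working from the current text would have to choose between two defensible populations, possibly after seeing the data.

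**Working it through.** **1. The plan's own figure.** Inputs from section 13.0: difference 12 h, SD 23.7 h, two-sided 0.05, 80% power. The normal approximation gives 2 × (1.96 + 0.8416)² × (23.7/12)² = 61.2, so 62 per group. The exact noncentral-t calculation gives 62.2, so 63, with 80.5% power at 63. Then 63/0.9 = 70. The stated 63 and 70 reproduce.

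**2. Two readings of *treatment*.**

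| Reading | Support in the documents | Effect of the rule |
|---|---|---|
| Prunes | Sections 3.5 and 3.6 call the prune arm the treatment arm; 6.3 and 13.0 set treatment against control; the agent table in 7.2 lists only prunes; the first removal criterion in 7.3 is prune intolerance | Zero-prune women can leave one arm only |
| Assigned regimen including docusate | Section 2.0 contrasts "women treated with prunes and docusate compared to those treated with docusate alone"; section 13.0 says "The sample size of 63 participants per treatment group was calculated"; section 3.5 gives docusate to everyone | Nearly every woman in both arms has begun; effect negligible |

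**3. Size under the prunes reading.** The documents give neither input needed, so both are assumed: f, the share of women who would never start prunes, and D, the amount by which their mean time differs from that of starters. With no true effect, the control mean is μ + fD. The prune arm after removal has mean μ. The bias is therefore f × D.

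Type I error comes from simulation: 1,000,000 replicates, pooled t-test, 70 randomised per arm, SD 23.7 h, removal from the prune arm only.

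| f | D (h) | Bias f × D (h) | Type I error |
|---|---|---|---|
| 3% | 12 | 0.36 | 0.051 |
| 5% | 12 | 0.60 | 0.052 |
| 5% | 24 | 1.20 | 0.059 |
| 10% | 24 | 2.40 | 0.087 |
| 10% | −24 | −2.40 | 0.087 |

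A normal approximation gives 0.053 for the second row and 0.090 for the fourth, so the simulation is in line. In the extreme case, 2.4/12 = 20% of the target difference. Removing non-starters from both arms, or keeping everyone, gives bias 0 and type I error 0.050.

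**4. How much outcome recovery matters.** If a fraction r of the prune arm's non-starters supply an outcome and all controls do, the remaining bias is D × [f − fr/(1 − f + fr)]. At f = 10% and D = 24 h:

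- r = 0.5: 24 × (0.10 − 0.05/0.95) = 1.14 h, type I error 0.058.
- r = 0.8: 24 × (0.10 − 0.08/0.98) = 0.44 h, type I error 0.051.
- r = 1: bias 0.

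**5. What a day 3 call can recover.** Section 1.1 gives 4 ± 1.5 days to first bowel movement without intervention. If the spread is an SD and times are normal (both assumed), z = (3 − 4)/1.5 = −0.67, so about 25% would have had a bowel movement by day 3. Docusate may raise that share, but many answers would still be not yet.

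**6. Dilution if everyone is kept.** Assume that 12 h is the effect at full uptake and that non-starters gain nothing. The effect becomes 12 × (1 − f): 11.64 h at 3% and 11.4 h at 5%. Power at 63 analysed per group falls from 80.5% to 78.1% and 76.4%.

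**The case against.** The sentence says who will be included; it does not say that anyone is dropped. A reader might infer that the plan prescribes a per-protocol analysis. The documents do not support that. Women who start and then cut back or stop prunes, as section 8.2 allows, stay in. Removal from treatment under section 7.3 is not removal from analysis. The two-thirds compliance threshold in section 10.0 defines an endpoint and is not used to exclude anyone. Only women with zero prune intake are at risk.

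Those women should be few. The screening questionnaire in Appendix III excludes women unwilling or unable to take prunes, and inability to start oral intake is checked immediately before randomisation.

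The larger figures also need strong inputs. A 24 h difference is about one SD. Taking 63 per arm instead of 70, the 10% and 24 h case gives 0.083. With an SD of 36 h (the 1.5 days in section 1.1, as an alternative assumption) at 63 per arm, it gives 0.064, and the 5% and 24 h case gives 0.055.

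All of this stands, and it limits the size of the problem. It does not settle which population is meant: both readings in the table have textual support, and nothing in the plan chooses between them.

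**Conclusion.** The point holds as a defect in the rule, with a small likely effect. The only analysis-set statement rests on an undefined event after randomisation, and one of its two plausible readings breaks the randomised comparison. Under that reading, assumed inputs of 3% to 5% non-starters and a 12 h difference give 0.4 to 0.6 h of bias and leave type I error close to 0.05. The 10% and 24 h case is an illustration of an extreme, neither a forecast nor a bound. If docusate counts as treatment, the effect is negligible.

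A reader might infer that the rule favours prunes. The documents give no non-starter rate and no outcome difference, so the sign is unknown. A reader might also infer from the dilution figures that the trial needs more women. Section 13.0 calls 12 h a clinically significant mean difference and does not say that it applies only to women who take prunes, so that inference is not supported either.

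**What to change.** Replace the sentence in section 10.0 with: *The primary analysis includes all randomised participants in the arm assigned, whether or not they took any prunes or docusate.* Then:

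- Seek the outcome sheet from non-starters as from everyone else.
- Report by arm the numbers known to have taken no prunes or no docusate, and the number unknown. These counts come from the same mailed survey.
- Keep any set of starters, or of women who ate two-thirds of their prunes, as secondary.

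The call in section 3.6 is described only as "inquiring about whether the participant has mailed the data collection sheets back". The masked caller may also ask for the date and time of the first bowel movement, and nothing about prunes, so that masking holds. This is a supplement only. The call is on day 3 and is repeated only if unanswered (the next day in section 3.6, day 5 in section 9.0), so it will miss women whose bowels have not yet moved and cannot be relied on to recover most outcomes. How those women, and unreturned sheets in general, enter the t-test is a separate issue.

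The cost is one sentence, an optional question on a call already planned, and the possible loss of power in step 6 if its two assumptions hold. The test itself and the enrolment target stay as they are.
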